### **Secondary endpoint analyses – Non-glycemic:**

- All of following metrics will be generated from the closed-loop and usual care periods and the differences will be reported unless otherwise specified:
- Number of carbohydrate interventions for hypoglycemia (day and night)
- Total number of grams of carbohydrate taken for hypoglycemia (day and night)
- Insulin total daily dose
- Mean daily basal insulin dose
- Mean daily bolus insulin dose
- Number of carbohydrate interventions for hypoglycemia during the daytime (7:00 AM – 11:00 PM)
- Total number of grams of carbohydrate taken for hypoglycemia during the daytime ((7:00 AM – 11:00 PM)
- Number of carbohydrate interventions for hypoglycemia overnight (11:00 PM – 7:00 AM)
- Total number of grams of carbohydrate taken for hypoglycemia overnight (11:00 AM – 7:00 AM)
- Mean meal carbohydrate content
- The following metrics will be generated from the closed-loop period:
- Insulin lispro dosing (u/kg/24 hours)
- Glucagon dosing (mcg/kg/24 hours)
- Fraction of time bionic pancreas in open-loop mode due to loss of CGM signal
- Fraction of time bionic pancreas completely off-line
- Fraction of time bionic pancreas off-line or not functioning properly for each of the following reasons: system crash, communication problem between CGM and bionic pancreas, communication problem between bionic pancreas and pumps, pump malfunction, tubing occlusion, infusion set failure/pulled out
- Difference in mean insulin dose per hour during periods of normal operation vs. periods of bionic pancreas downtime
- Fraction of bionic pancreas downtime during which automatic basal rate suspended or reduced
- Difference in mean insulin dosing during the four hour period after a meal during periods of normal operation vs. periods of bionic pancreas downtime (open-loop dosing)
- Difference of outcome measures on day 1 vs. remaining days (days 2-5) and on day 1-2 vs. on remaining days (days 3-5)
- All of following metrics will be generated from the closed-loop, usual care periods, and from the non-participants and the differences will be reported unless otherwise specified:
- Number of carbohydrate interventions for hypoglycemia (day and night)
- Total number of grams of carbohydrate taken for hypoglycemia (day and night)
- Insulin total daily dose
- Mean daily basal insulin dose
- Mean daily bolus insulin dose
- Number of carbohydrate interventions for hypoglycemia during the daytime (7:00 AM – 11:00 PM)
- Total number of grams of carbohydrate taken for hypoglycemia during the daytime ((7:00 AM – 11:00 PM)
- Number of carbohydrate interventions for hypoglycemia overnight (11:00 PM – 7:00 AM)
- Total number of grams of carbohydrate taken for hypoglycemia overnight (11:00 AM – 7:00 AM)

We will calculate means, median, percentages, standard deviations, standard errors, inter-quartile

ranges, and 95% confidence intervals in descriptive analyses. We will use paired t-test for comparison of means. We will use multivariate regression models with repeated measurements to compare means and percentages while adjusting for patient demographics characteristics (age, gender).

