#### **V. Study Procedures**

Note that these study procedures apply only to study participants. The involvement of consenting non-participants will be limited to a retrospective review of their chart. They will have no direct contact with study staff, will interact with study devices or drugs, and there will be no modification or real-time monitoring of their camp care.

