### **Mild hypoglycemia (mild signs and symptoms or BG 60–80 mg/dl, able to self treat):**

- Give 15 gm of rapid-acting carbohydrates (glucose tabs, juice, milk, gel, etc.)
- Wait 15–20 minutes and recheck BG
- If BG is >70 mg/dl, give 15 grams of complex carbohydrate (typically snack crackers with peanut butter or cheese). Omit the 15 grams of complex carbohydrate if a meal or snack is scheduled within one hour.
- If BG is <70 mg/dl, restart treatment algorithm

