#### **V. e. Response to Hypoglycemia**

- All subjective symptoms of hypoglycemia will be investigated with a capillary BG using a HemoCue meter.
- Volunteers in both of the study arms (closed-loop and usual care) will take carbohydrates to treat hypoglycemia or symptoms consistent with hypoglycemia according to a protocol modified from the usual camp protocol as follows:
- Mild hypoglycemia (mild signs and symptoms or BG 60–80 mg/dl, able to self treat):
  - Wait 15–20 minutes and recheck BG
  - If BG is still < 70 give 15 gm of rapid-acting carbohydrates (glucose tabs, juice, milk, gel, etc.)
- The modified hypoglycemia protocol is intended to allow auto-treatment of mild hypoglycemia with glucagon by the control algorithm to occur without being preempted by carbohydrates given prior to the onset of hypoglycemia (for instance in the 70-80 mg/dl range) or when hypoglycemia is mild (BG 60-70 mg/dl). In order to maintain safety, a second BG check in 15-20 minutes is included so that hypoglycemia is treated if not averted by the closed-loop system.
- For experimental validity, the same modifications from camp policy need to be used for both the closed-loop and open-loop arms of the study. Note that treatment of BG < 60 mg/dl will be according to the normal camp protocol in both arms (immediate treatment with rapid-acting carbohydrates) AND subjects may take carbohydrates at any time for symptoms when BG is < 80 mg/dl
- Camp healthcare providers and camp counselors will carry rapid acting and complex carbohydrate interventions with them at all times. All carbohydrate treatments for hypoglycemia will be documented by study staff (amount and time).
- In any case in which two rapid-acting carbohydrate interventions must be administered by camp protocol or if glucagon is administered manually by injection, a study staff member will check the operation of the bionic pancreas system. Consideration will be given to replacing the glucagon infusion set and/or recalibrating the CGM.

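### Carbohydrate interventions and grams for hypoglycemia are compared with non-participants, who are treated under a different rule and checked differently, so the contrast cannot be read as a device or study effect

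*Combined protocol and SAP*

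**What the plan says.** The non-glycemic part of VI. b ends with a list of metrics to be produced "from the closed-loop, usual care periods, and from the non-participants and the differences will be reported unless otherwise specified". The list includes "Number of carbohydrate interventions for hypoglycemia (day and night" and "Total number of grams of carbohydrate taken for hypoglycemia (day and night", each repeated for daytime and for overnight. That makes six metrics: three counts and three gram totals.

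The three groups do not share a treatment rule at BG 60–80 mg/dl:

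- **Non-participants.** Section V limits their involvement to chart review and states that "there will be no modification or real-time monitoring of their camp care". They stay on the camp policy summarised in V. d. ii. Its first step for mild hypoglycemia is "Give 15 gm of rapid-acting carbohydrates (glucose tabs, juice, milk, gel, etc". After a recheck at 15–20 minutes, if BG is above 70, the next step is "give 15 grams of complex carbohydrate (typically snack crackers with peanut butter or cheese", left out when food is due within the hour.
- **Both study arms.** Section V. e replaces this with a wait of 15–20 minutes and a recheck, then "If BG is still < 70 give 15 gm of rapid-acting carbohydrates". No complex-carbohydrate step is listed. Volunteers may take carbohydrate for symptoms at any time when BG is below 80.

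Below 60 mg/dl, V. e says: "Note that treatment of BG < 60 mg/dl will be according to the normal camp protocol in both arms".

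**The concern.** A count of treatments, or of grams given as treatment, measures hypoglycemia across groups only if the trigger for treatment is the same. Here one glucose value can be an intervention in a non-participant and no event in a volunteer.

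The protocol accepts this principle. Section V. e explains that the modification is there so that carbohydrate does not pre-empt automated glucagon, and that both study arms must use it for the experiment to be valid. VI. b then adds a third group to which it does not apply, with no restriction or caveat. The planned regression adjusts for age and gender, which cannot remove a difference in treatment rule.

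At stake is the reading of the closed-loop versus non-participant difference, part of which the rule produces whatever the device does. The usual-care versus non-participant difference has the same problem with no device involved.

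**Working it through.** The plan gives no figure for this contrast, and VI. c says there is no formal power analysis. The check therefore compares the two rules directly.

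**1. Single readings, no symptoms**

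| BG course | Camp rule | Study rule |
|---|---|---|
| 75, stays at or above 70 | 1 intervention, 15 g, or 30 g with the complex step | 0 interventions, 0 g |
| 65, at 72 on recheck without treatment | 1 intervention, 15–30 g | 0 interventions, 0 g |
| Below 60 | Camp protocol | Camp protocol |

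**2. Per 100 readings of 60–80 mg/dl with the same BG course, first treatment step**

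Inputs: s is the share treated at once for symptoms under the study rule; p is the share of the rest still below 70 on recheck. The documents give neither, so both are assumed over a range.

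- Camp rule: 100 interventions and 100 × 15 = 1500 g rapid carbohydrate, up to 3000 g if every one also draws 15 g of complex carbohydrate.
- Study rule: interventions = 100 × (s + (1 − s) × p); grams = 15 × interventions.

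| s | p = 0.2 | p = 0.4 | p = 0.6 | p = 0.8 | p = 1.0 |
|---|---|---|---|---|---|
| 0 | 20 (300 g) | 40 (600 g) | 60 (900 g) | 80 (1200 g) | 100 (1500 g) |
| 0.25 | 40 (600 g) | 55 (825 g) | 70 (1050 g) | 85 (1275 g) | 100 (1500 g) |
| 0.5 | 60 (900 g) | 70 (1050 g) | 80 (1200 g) | 90 (1350 g) | 100 (1500 g) |

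At this step the study rule never gives more than the camp rule. It gives the same number only when every symptom-free reading is still below 70 on recheck. Treatment for symptoms narrows the gap but does not close it.

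**3. Illustration per non-participant over five days**

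- Readings: six a day (the lower end of the six to seven in the HemoCue section of V. c) × 5 = 30.
- Share at 70–80 mg/dl: 3–8%, assumed.
- Extra interventions: 0.03 × 30 = 0.9 to 0.08 × 30 = 2.4, if these readings stay at or above 70 without symptoms.
- Lower gram figure, no complex step: 0.9 × 15 = 13.5, about 14 g.
- Upper gram figure: four checks a day come 10–30 minutes before a meal or snack (V. d. ii), so 4 × 5 = 20 of the 30 readings draw at most 15 g. Spread evenly, 2.4 × (2/3 × 15 + 1/3 × 30) = 2.4 × 20 = 48 g.
- With five checks a day, as in the BG Testing summary, there are 25 readings, and the upper figure is 0.08 × 25 × (0.8 × 15 + 0.2 × 30) = 2.0 × 18 = 36 g.

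These amounts shrink if some readings fall below 70 and are treated, or are treated for symptoms.

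**4. Differences in detection, which may act the other way**

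- Volunteers in both arms: a 3:45 AM check whatever the midnight value, alert-driven checks from 11 PM to 7 AM, and round-the-clock telemetry (V. d. iii).
- Non-participants: a 3:00 AM check only if the midnight check needed intervention, plus any the camp physician orders (V. d. ii).

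More lows can therefore be found and treated in volunteers, particularly overnight, which is reported separately. Waiting before treatment may also let some lows deepen. The documents give no figures to weigh these effects against the rule effect.

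**The case against.** The strongest reply is that the direction of the result is not known. A reader might infer from the two rules that volunteers will show fewer interventions and grams, so that the comparison is tilted towards the study arms. The documents do not support that: it follows only if detection is also equal, and detection differs in a way that can raise the volunteers' counts. This objection stands. It does not rescue the contrast, because it adds a second reason why the groups are not comparable.

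A reader might also take the study rule to bar treatment unless the recheck is below 70. Section V. e does not say so, because it allows carbohydrate for symptoms below 80.

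It can further be said that the consequence is limited. The contrast is non-randomised and one of many secondary analyses. Non-participants enter neither the co-primary endpoints nor the success criteria in VI. d. The usual-care arm shares the modified rule, so a gap between it and non-participants would itself signal a non-device effect. All of this is right, and it keeps the point small. It does not make the listed differences interpretable, and VI. b does not tell the reader to use the usual-care arm in this way.

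Finally, restricting the comparison to treatments below 60 mg/dl may look like a clean repair. It is not. Whether a camper reaches 60 depends on whether a reading of 65 was treated at once or after a wait, and on how often BG is checked. The text for this stratum also differs and should be reconciled: the camp policy allows glucose or low-dose glucagon, while V. e describes it as rapid-acting carbohydrate.

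**Conclusion.** The concern holds in a limited form. The treatment rule differs between non-participants and both study arms, the two metrics depend directly on it, and VI. b makes no allowance for this. With identical glucose and detection, the rule alone lowers interventions and grams in the study arms. Since detection also differs, the net bias is undetermined, and the contrast cannot be interpreted as an effect of the device or of study participation.

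The size is illustrative only: about 0.9–2.4 interventions and 14–48 g per non-participant over five days, resting on the assumed 3–8% of 30 readings. Multiplying 2.4 by 30 g to reach 72 g would ignore the omission of the complex carbohydrate before meals and snacks.

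The closed-loop versus usual-care contrast is not affected by this rule difference, since both arms follow V. e. The co-primary endpoints do not use non-participants.

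**What to change.** In the non-glycemic part of VI. b:

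1. Remove the between-group difference, and any test or interval for it, for carbohydrate interventions and grams (overall, daytime and overnight) wherever non-participants are included.
2. Report these metrics for non-participants as description only, split by BG at treatment (below 60 and 60–80 mg/dl) where the chart records it.
3. State beside the table that the treatment rule and the BG checking differ between non-participants and volunteers. Do not present the stratum below 60 as an unbiased comparison.
4. Keep the full closed-loop versus usual-care comparison.

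No clinical rule needs to change. The cost is a wording change and the loss of one non-randomised secondary contrast. The split depends on the chart: VI. a lists, for non-participants, the number of interventions, the nadir BG per event and estimated carbohydrate intake, but not BG at treatment or grams taken for hypoglycemia. If the charts do not hold these, the split and the gram totals should be dropped for that group.

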In our first trial of this type, which began in February, 2013, adult research volunteers stay in a hotel at night and have freedom of movement in the downtown Boston area during the day. They have minimal restrictions on their activities, food intake, exercise, and schedule over a closed-loop control period of five continuous days to fully test the capabilities of the bionic pancreas device. Despite the great degree of freedom that research volunteers have during the study period, they also have very close supervision by nurses who stay with them at all times and monitor them around the clock for safety. This study, called the Beacon Hill Study, has been approved by the FDA and the MGH Institutional Review Board (IRB) and will conclude in June, 2013.

The current study is designed to test the capabilities of the bionic pancreas system in youth in a realistic, challenging environment with close supervision for safety. We have chosen the diabetes camp environment for this study because it will present the bionic pancreas with challenges to blood glucose control that are as great or greater than would be faced in the daily life of children with diabetes, yet affords the opportunity for close supervision and monitoring of multiple children participating in the study simultaneously. This study is planned for June through August of 2013 at the Joslin Diabetes Camp (boys) and the Clara Barton Diabetes Camp (girls).

Recently, a study using a closed-loop system to do nighttime-only closed-loop control was published (30). This trial compared closed-loop control to usual care for one night each in a cross-over design in 56 volunteers. This study found less hypoglycemia and a trend towards lower BG in the closed-loop group, although the latter trend did not reach statistical significance. Our study is considerably more ambitious; 32 volunteers will each participate in five days of closed-loop and five days of usual care in a crossover design for 160 nights and days of closed-loop control. Notably, daytime control is considerably more challenging as glucose disturbances caused by meals and exercise must be managed by the bionic pancreas system.

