### **Aim 1. To test the safety and efficacy of the bi-hormonal closed-loop bionic pancreas that is mobile, wearable, and adaptive in regulating BG in youth 12-20 years of age in a diabetes camp environment.**

The bionic pancreas will be compared to usual care in a crossover design in which each volunteer will serve as his or her own control. Each volunteer will be under closed-loop glucose control for five days and usual camp level of diabetes care for five days in random order with a one day washout period in between. The study will be carried out at the Clara Barton Diabetes Camp and the Joslin Diabetes Camp. Both camps are in North Oxford, MA and both are managed under the Barton Center for Diabetes Education with an integrated health care team and Medical Directors. Volunteers will participate in the usual camp activities during the day, will eat the usual camp meals, and will stay in camp cabins at night. They will be fully integrated into the non-study population and will have blood glucose monitoring as usual during both closed-loop and usual care periods except that 3:00 AM BG check that is sometimes done in normal camp care will be replaced by a 3:45 AM check done routinely in study volunteers. In addition, capillary BG checks for study volunteers will be tested using a highly accurate, laboratory equivalent meter (HemoCue). Blinded continuous glucose monitoring will be done during the usual care period. During the entire experiment, the CGM data of all volunteers will be continuously monitored by study staff around the clock using telemetry. The primary outcome measures will be the difference between closed-loop and usual care in mean blood glucose and the fraction of BG measurements  $< 70$  mg/dl. Secondary outcomes will include the same measures as defined by CGM, and CGM accuracy, as well as hypoglycemia requiring intervention with carbohydrate or rescue glucagon.

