#### **IV. a. Number of Subjects**

It is expected that we will have 32 volunteers, 16 females and 16 males, complete full-length closed-loop experiments (5 days of closed-loop BG control). We will attempt to recruit participants in roughly equal numbers in the following age cohorts: 12-13 years, 14-16 years, and 17-20 years. We expect that the experiments can be accomplished over a period of 4-6 months. Up to 64 volunteers with type 1 diabetes will be enrolled, 32 females and 32 males. The upper bound is based on the expectation that some volunteers will be excluded after the screening visit and the possibility that some experiments may have to be discontinued before completion (due to, for instance, intercurrent illness or subject withdrawal). Studies will be conducted sequentially at the two proposed sites.

We will also ask non-participants meeting who are attending camp at the same time and who meet key criteria for study inclusion (age 12-20, use of insulin pump) for permission to review their camp records and to document pre-meal, pre-snack, bedtime, and midnight glucose values, as well as glucose interventions for hypoglycemia, and to get the result of their last A1c test prior to attending camp.

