**V. d. Experimental Procedures and Data Collection****V. d. i. Screening Visit:**

- All volunteers will have a screening visit to confirm eligibility.
- The volunteer will be interviewed and the case report form will be completed by a study nurse or study physician to establish whether the volunteer is eligible to continue with the screening.
- If a laboratory hemoglobin A1c drawn within 3 months of the time of screening is not available, one will be obtained.
- A study physician or nurse practitioner will review the case report form and laboratory result to determine volunteer eligibility.
- The screening visit may be performed over the phone
- The order of the usual care monitoring and closed-loop visits will be randomized in blocks of two volunteers.

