**V. d. iii. Study-specific Procedures**

**Closed-loop and Usual Care Visit Day 0 – DexCom G4 Platinum Sensor Placement:**

- Volunteers will check in to the camp the day before the start (Saturday) at 11:00AM.
- Up to 8 volunteers may perform a closed-loop experiment at the same time and be integrated with the other campers’ accommodations. During bedtime hours study staff will have the ability to access all cabins so that they can respond to any issues or emergencies that may arise.
- Volunteers will bring any routinely used medications. The camp will be responsible for dispensing medications other than insulin and glucagon during the closed-loop portion of the experiment. During usual care, all medications will be dispensed by the camp.

- Any medical advice needed by the volunteers during their participation that is not directly related to BG control during the experiment should be obtained by them in the usual manner at camp.
- Subjects may take any over-the-counter medications that are recommended by the camp physician during the trial except acetaminophen, which will not be allowed due to potential interference with CGM sensing.
- If a volunteer develop an illness during the experiment camp guidelines will be used for sick day management. If vomiting occurs, a study physician or nurse practitioner will be notified and will evaluate the volunteer in person.
- Female volunteers post-menarche will provide a urine sample for urine pregnancy testing. If the test is positive the volunteer (and legal guardian if less than 18 years of age) will be informed of the result by the study staff and they will be excluded from participating.
- Height, weight, blood pressure and temperature will be measured. A brief history and physical will be performed by a study physician or nurse practitioner.
- The DexCom G4 sensor will be placed by 1:00 PM and linked to the CGM receiver in the bionic pancreas control unit. For volunteers in the control arm the bionic pancreas control unit will have a modified interface that does not report CGM glucose, but does include an interface to allow entry of BG values.
- Initial calibration (at 2 hours after placement, at approximately 3:00 PM) will be performed by the study staff using the HemoCue meter.
- An additional calibration will be performed before dinner.
- Volunteers have their BG managed according to usual camp protocols until the following day.

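### The crossover analysis names no period term; adding period within camp is an inexpensive precision safeguard, not a correction of bias

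*Combined protocol and SAP*

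**What the plan says.** Aim 1 sets the design: "Each volunteer will be under closed-loop glucose control for five days and usual camp level of diabetes care for five days in random order". Under V. d. i. (Screening Visit), "The order of the usual care monitoring and closed-loop visits will be randomized in blocks of two volunteers". The section on transition between study arms has every volunteer change treatment in the second week.

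Section IV. a. sets the size: "It is expected that we will have 32 volunteers, 16 females and 16 males". It adds: "Studies will be conducted sequentially at the two proposed sites". Section I. d. places the study "at the Joslin Diabetes Camp (boys) and the Clara Barton Diabetes Camp (girls"). The Day 0 procedures add a capacity limit: "Up to 8 volunteers may perform a closed-loop experiment at the same time".

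The co-primary endpoints in VI. b. are the closed-loop minus usual-care differences in mean HemoCue glucose and in the percentage of those readings below 70 mg/dl. The inferential plan is two sentences at the end of VI. b.: "We will use paired t-test for comparison of means" and "We will use multivariate regression models with repeated measurements to compare means and percentages while adjusting for patient demographics characteristics (age, gender"). The second is the only method expressly assigned to percentages. No section names a term for period, week, sequence or camp. The comparisons of day 1 with later days concern days within a treatment period, not week 1 against week 2.

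**The concern.** In a two-period crossover, anything that makes the second week differ from the first for everyone (activities, menu, weather, insulin settings after check-in) enters the paired difference with opposite signs in the two sequences. A paired t-test leaves that in the residual. Age and gender do not change within a volunteer, so with complete pairs adjusting for them does not remove it.

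Because the camps run one after the other, week 1 at one camp is a different calendar week from week 1 at the other. A single common period term would protect only against a week effect that both camps share.

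At stake is precision for both co-primary comparisons in a trial of 32, and through them the superiority route to success in VI. d. The other route there, based on absolute thresholds, does not use this comparison.

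**Working it through.** **Inputs from the documents:** 32 completers, 16 per camp (IV. a. with I. d.); order randomised in blocks of two (V. d. i.), hence 8/8 per camp if balanced. At up to 8 on closed-loop at once, one two-week session holds 16, so one session per camp is enough if all complete.

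**Assumed:** two-sided 5% level; SD of paired differences 20 mg/dl, treatment effect 12 mg/dl, week effect 0 to 10 mg/dl. VI. c. gives no such figures, and the plan states no power to reproduce.

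**Model.** Let *d* be closed-loop minus usual care, τ the treatment effect and δ the week 2 minus week 1 difference. Then *d* = τ − δ + error for closed-loop first, and *d* = τ + δ + error for usual care first.

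**Step 1: balanced sequences.** The two δ terms cancel in the mean, so the paired estimate is unbiased. Its SE is inflated by √(1 + k² × 32/31), with k = δ/SD:
- k = 0.25: √(1 + 0.0625 × 1.0323) = 1.032
- k = 0.5: √(1 + 0.25 × 1.0323) = 1.122

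The 95% half-width is t × 20 × inflation / √32, with t = 2.0395 (31 df) for paired. Period within camp has no inflation and t = 2.0452 (29 df). Size and power are simulated (200,000 trials per scenario).

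| Week effect, both camps | Half-width, paired | Half-width, within camp | True size, paired | Power, paired | Power, within camp |
|---|---|---|---|---|---|
| 0 | 7.21 | 7.23 | 5.0% | 90.8% | 90.6% |
| 5 mg/dl (0.25 SD) | 7.44 | 7.23 | 4.3% | 89.5% | 90.6% |
| 10 mg/dl (0.5 SD) | 8.09 | 7.23 | 2.9% | 86.0% | 90.6% |

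Break-even for period within camp is k = √[((2.0452/2.0395)² − 1) × 31/32] ≈ 0.07.

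**Step 2: common period or period within camp.** Under the same assumptions, power for paired / common period / period within camp is 88.4 / 89.5 / 90.5% with a week effect of 10 mg/dl at one camp only, and 85.9 / 85.7 / 90.6% with +10 at one camp and −10 at the other. If the effect is the same at both camps, the two adjusted models are equivalent to within about 0.1 point.

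**Step 3: unbalanced completers.** With n1 closed-loop first and n2 usual care first, the paired estimate shifts by δ × (n2 − n1)/N. At 14/18 that is δ × 4/32 = 12.5% of δ, or 0.6 mg/dl for δ = 5 and 1.25 mg/dl for δ = 10. Simulated type I error of the paired test at 14/18 is 4.8% and 3.9%, still below 5%.

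**Step 4: cost of the term.** Balanced with no week effect: 2.0452/2.0395 = 1.003. If unbalanced, the SE ratio is √(32 / [32 − Σ(difference in cell sizes)²/camp size]):
- 7/9 at both camps: √(32/31.5) = 1.008
- 6/10 and 8/8: √(32/31) = 1.016

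**Step 5: a make-up session.** Suppose the cells are 8/7, 7/8 and a make-up session of 2/0. Fitting period within session gives √(32 / [32 − 1/15 − 1/15 − 4/2]) = √(32/29.87) = 1.035. The 2/0 session then contributes nothing to the treatment estimate. Pooled with the 7/8 session of its camp, the cells become 8/7 and 9/8, and the ratio is √(32 / [32 − 1/15 − 1/17]) = 1.002.

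**The case against.** The strongest reply is that the design already deals with a week effect: order is randomised in small blocks, both treatments run in the same week, and everyone switches. The paired t-test is then valid, at worst slightly conservative, and preferring an adjusted model is close to taste. This stands as a limit on how much the point matters. At 0.25 SD the gain is about one point of power.

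The effect size, SD and week effect are also assumed, VI. d. gives no level or test for superiority, and nothing in the documents shows that week effects differ between camps. All of that stands.

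Three stronger readings are tempting and not supported:
- A reader might infer that the paired analysis is biased or invalid. With balanced sequences it is neither, and at 14/18 its type I error stays below 5% in the cases examined.
- A reader might infer that the regression excludes period. The text is only silent: its parenthesis lists demographic characteristics, and period is not one, so the term may be intended.
- A reader might infer a real week effect from the opening-day reduction of basal rates in the camp-policy summary (V. d. ii.). That makes one plausible, but the documents give no evidence of its existence or size.

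The term is also not cheap in every layout: a sparse make-up session with its own period term can cost more (3.5% in SE) than is gained at 0.25 SD.

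**Conclusion.** The point holds as a minor, optional improvement. No period term is named for either co-primary comparison, and the named covariates cannot stand in for one. The consequence is lost precision if a week effect exists, plus a small shift if completers are unbalanced by sequence. It is not a validity flaw. The sizes in the working rest on assumed week effects of 0.25 to 0.5 SD; below about 0.07 SD the term does not pay for itself. Naming the model in advance also removes a later choice between an adjusted and an unadjusted analysis.

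**What to change.** In VI. b., state for both co-primary endpoints that the model has treatment and period (week 1, week 2) within camp as fixed effects and volunteer as random effect, and that the treatment difference is reported with its 95% CI. For readings below 70 mg/dl, analyse each volunteer's percentage per period, so the result stays in percentage points. Age can stay. If boys attend one camp and girls the other, the existing gender term is already the camp main effect; only period and its interaction with camp are new.

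If a small make-up session is needed, pool it with that camp's main session for the period term. This assumes a similar week effect in both sessions. If a re-randomisation check is added for the percentages, it should follow the actual blocks of two.

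The cost is one sentence and 2 degrees of freedom, with no new data. The price in precision is about 0.3% of CI width when sequences are balanced and there is no week effect, and 0.8% to 1.6% in SE for the 14/18 splits shown.
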